22 APPENDICES

22.1 Appendix 1 –Schedule of Events – Visit 1 (In ED, inpatient unit or Outpatient Clinic within 7 days (168 h) after OD

Procedure / Assessment	Screening Procedures (Visit 1)	Treatment Period (Visit 1)			Sublocade Dosing	Post-Sublocade dose Procedures
		Pre-Suboxone dose Procedures	Suboxone Dosing	Post-Suboxone dose Procedures		
Informed Consent	X					
Inclusion/Exclusion Criteria	X					
Demographics	X					
Medical History	X					
Brief Physical Examination	X					
Concomitant Medications Assessment	X					
Vital Signs	X					
Height/Weight/BMI	X					
Breathalyzer	X					
Urine Pregnancy Test	X ^b					
DSM-5 OUD/AUD/SUD Checklist	X					
Liver function laboratory tests (STAT)		X ^d				
COWS		X ^e		X		X
OC-VAS		X ^e		X		
Delay Discounting Task		X		X		
Opioid Demand Task		X		X		
SUBOXONE Test Dose			X ^{f,g}			
SUBLOCADE Dose					X	
PGx Sampling				X ^a		
AE Assessment		X		X ^g		X
Clinic appointment visit scheduled for next dose						X

AE = adverse event; COWS = Clinical Opiate Withdrawal Scale; MINI = Mini-International Neuropsychiatric Interview

- a. PGx samples will only be taken from subjects that consent to participate in the optional PGx sub-study.
- b. Urine pregnancy test, only for females of child-bearing potential. Results must be available and reviewed prior to Suboxone treatment.
- c. Subjects will be included in the study only after it is determined that subject meets all inclusion criteria and none of the exclusion criteria.
- d. STAT Local labs will be used for screening liver function tests. Samples must be drawn prior to dosing and will include ALT, AST and bilirubin. Abnormal liver function tests (LFTs) will be followed at clinic visits according to investigator's judgement. Liver function tests obtained for clinical reasons will also be used for research purposes if we are unable to obtain blood for research purposes. An etiological evaluation will be performed if a hepatic adverse event is suspected.
- e. The COWS and OC-VAS will be completed after consent but prior to first administration of SUBOXONE sublingual film.
- f. Day 1 SUBOXONE/SUBLOCADE Regimen includes supervised administration of 4mg/1 mg SUBOXONE sublingual film, followed by 300 mg SUBLOCADE administration.
- g. Subjects will be assessed for adverse events predose and 1-2 hours postdose depending on RASS score prior to discharge.

22.2 Appendix 2 – Treatment Clinic Schedule of Events – (Week 1 Day 2 – Week 25 Day 169)

Procedure / Assessment	Treatment Period									
	Visit 2	Visit 3	Visit 4	Visit 5	Visit 6	Visit 7	Visit 8	Visit 9	Visit 10	Visit 11
	Wk 1 D 2 (-0/+3) D	Wk 2 D 8 (-0/+4) D	Wk 3 D 15 ±4 D	Wk 4 D22 (±4) D	Wk 5 D29 (±4) D	Wk 6 D36 (-2/+4) D	Wk 7 D43 (±4) D	Wk 8 D50 (±4) D	Wk 9 D57 (±4) D	Wk 10 D64 (-2/+4) D
Counselling	X	X	X	X	X	X	X	X	X	X
Urine Drug Screen	X	X	X	X	X	X	X	X	X	X
COWS	X	X	X	X	X	X	X	X	X	X
MINI International Neuropsychiatric Interview	X									
Delay Discounting Task	X									
Opioid Demand Task	X									
OC-VAS ^a	X	X	X	X	X	X	X	X	X	X
TEA	X		X							
HCRUQ	X		X				X			
MSQ	X		X							
WPAI:SHP	X									
AE Assessment	X	X	X	X	X	X	X	X	X	X
Concomitant Medications Assessment	X	X	X	X	X	X	X	X	X	X
Brief Physical Examination	X									
Vital Signs	X	X	X	X	X	X	X	X	X	X
Urine Pregnancy Test ^b	X	X	X	X	X	X	X	X	X	X
SUBLOCADE Injection		X				X				X
Liver function lab tests	X				X				X	
Laboratory Tests	X									

HCRUQ = Health Care Resource Utilization Questionnaire; WPAI:SHP = Work Productivity and Activity Impairment Questionnaire: Specific Health Problem

- a. OC-VAS will be assessed prior to SUBLOCADE injection
- b. Urine pregnancy test, only for females of child-bearing potential. Results will be obtained prior to SUBLOCADE injection.

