5.3 Exclusion Criteria

A subject will not be eligible for inclusion in this study if any of the following criteria apply:

1. Current diagnosis, other than OUD, requiring chronic opioid treatment.
2. Active suicidal ideation in opinion of the Investigator or designee.
3. Female subject that is lactating, pregnant or planning to become pregnant during their participation in the study.
4. Uncontrolled intercurrent illness including, but not limited to, psychiatric illness/social situations that would limit compliance with study requirements or compromise the ability of the subject to provide written informed consent, signs of opioid toxicity more than 2 hours from naloxone administration or subjects with evidence of pulmonary edema.
5. Known allergy or hypersensitivity to SUBOXONE.
6. Any condition that, in the opinion of the Investigator would interfere with interpretation of subject safety or study results.

-
7. Currently receiving MAT for OUD (e.g. methadone, buprenorphine) or received methadone as a treatment for OUD within 30 days prior to consent.
 8. Concurrent treatment with another investigational agent.
 9. Concurrent enrolment in another clinical study, or observational study that includes MAT.
 10. Treatment for OUD required by court order.
 11. Current or pending incarceration/ legal action that could affect participation or compliance in the study.
 12. Subjects who are unable, in the opinion of the Investigator, to comply fully with the study requirements.
 13. Less than 48-72 hours since last use of long acting opioids (e.g., methadone), by self-report.
 14. Current intoxication with benzodiazepines or alcohol.
 15. Meet current DSM-5 diagnosis for severe Benzodiazepine or Alcohol Use Disorder, or endorse benzodiazepine or alcohol withdrawal symptoms.
 16. Current illicit opioid users who endorse regular use of long acting opioids (e.g. methadone).
 17. Total bilirubin $\geq 1.5x$ the upper limit of normal (ULN), alanine aminotransferase (ALT) $\geq 3xULN$, aspartate aminotransferase (AST) $\geq 3xULN$, serum creatinine $> 2xULN$, international normalized ratio (INR) $> 1.5xULN$
 18. Patients with a history of Long QT Syndrome or an immediate family member with this condition or those taking Class IA antiarrhythmic medications (e.g., quinidine, procainamide, disopyramide) or Class III antiarrhythmic medications (e.g., sotalol, amiodarone) or other medications that prolong the QT interval.

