6.4.5 Liver Chemistry Stopping Criteria

Liver chemistry stopping criteria 1-5 are defined below:

1. The subject has ALT or AST $>3 \times$ ULN **and** bilirubin $>2 \times$ ULN ($>35\%$ direct bilirubin) (or ALT or AST $>3 \times$ ULN **and** international normalized ratio (INR) >1.5 , if INR measured).
Note: if serum bilirubin fractionation is not immediately available, withdraw study drug for that subject if ALT or AST $>3 \times$ ULN and bilirubin $>2 \times$ ULN. Serum bilirubin fractionation should be performed if testing is available. If testing is unavailable, the presence of detectable urinary bilirubin on dipstick should be recorded, indicating direct bilirubin elevations and suggesting liver injury.
2. The subject has ALT or AST $>8 \times$ ULN.
3. The subject has ALT or AST $>5 \times$ ULN but $<8 \times$ ULN persisting for > 2 weeks.

4. The subject has ALT or AST >3 x ULN if associated with symptoms (new or worsening) believed to be related to hepatitis (such as fatigue, nausea, vomiting, right upper quadrant pain or tenderness or jaundice) or hypersensitivity (such as fever, rash, or eosinophilia).
5. The subject has ALT or AST >5 x ULN but <8 x ULN and cannot be monitored weekly for >2 weeks.

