8.5 Clinical Laboratory Tests

Clinical laboratory tests will be performed at the time points listed in the Schedule of Events ([Appendix 1](#) and [Appendix 2](#)) in a licensed clinical laboratory. Urine pregnancy tests and urine drug screens may be performed using a licensed point of care test (dipstick). Abnormal liver function tests (LFTs) will be followed at clinic visits according to investigator's judgement. An etiological evaluation will be performed if a hepatic adverse event (AE) is suspected.

Subjects are to be in a seated or supine position during blood collection.

The following clinical laboratory tests specified in Table 1 will be performed.

Table 1 List of Laboratory Tests

Hematology:	Serum Chemistry:
Hematocrit	Albumin
Hemoglobin	Alkaline phosphatase
Mean corpuscular hemoglobin	Alanine aminotransferase (ALT)
Mean corpuscular hemoglobin concentration	Amylase
Mean corpuscular volume	Aspartate aminotransferase (AST)
Platelet count	Blood urea nitrogen
Red blood cell count	Calcium
White blood cell count with 3-part differential	Calculated creatinine clearance
	Carbon dioxide
Pregnancy:	Chloride
Urine Pregnancy (only for females not postmenopausal or surgically sterile for at least 1 year)	Creatinine
	Creatine kinase and subtypes
	Gamma-glutamyl transferase
	Globulin
Additional Tests:	Glucose (non-fasting)
HIV	Lactate dehydrogenase
HCV B/C	Magnesium
Urine Drug Screen (UDS):	Phosphorus
Opioids	Potassium
Fentanyl	Sodium
Buprenorphine	Total bilirubin
Methadone	Direct bilirubin
Oxycodone	Total cholesterol
Amphetamines	Total protein
Cannabinoids	
Barbiturates	
Benzodiazepines	
Cocaine	
Methamphetamines	
Phencyclidine	
Breath alcohol test	

HIV = human immunodeficiency virus antibodies; HCB = Hepatitis B Virus; HCV = Hepatitis C virus.

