9.3 Drug Administration

9.3.1 SUBLOCADE Injection

SUBLOCADE injection will be administered following confirmation that the subject meets all eligibility and continuation criteria. The designated study treatment should be administered under the supervision of the Investigator, a suitably qualified member of the study team, or by a pharmacist. The Investigator or designee agrees not to administer SUBLOCADE from, or store it, at any location other than the study site agreed upon with the Indivior. Detailed instructions related to preparation of SUBLOCADE injection are outlined in the Prescribing Information.

SUBLOCADE subcutaneous (SC) injection sites should be rotated (see USPI for details) and the product must not be administered intravenously or intramuscularly. Eligible subjects will receive up to 7 subcutaneous injections of SUBLOCADE injection as outlined in the SOE ([Appendix 1](#) and [Appendix 2](#)). No injections are permitted outside of the protocol-specified window without the approval of the PI. Detailed instructions regarding the administration of SUBLOCADE injections are located in the USPI.

Time of dose is defined as the time the SUBLOCADE SC injection is complete. The time of dose and any dosing observations (e.g., partial doses or other issues with the injection) will be recorded in the source documentation; in addition, time of dose will be recorded in the eCRF.

The Investigator will not supply SUBLOCADE injection to any person except study personnel for SC injection of subjects in this study.

Adequate precautions must be taken to avoid direct contact with SUBLOCADE injection. Occupational hazards and recommended handling procedures are provided in the SUBLOCADE USPI.

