22.3 Appendix 3 – Liver Safety

Monthly monitoring of liver chemistry will occur during the study treatment period. The following should occur if a subject meets any of the liver chemistry stopping criteria as outlined in Section 6.4.5 of [000] of the protocol:

- Subject should immediately be withdrawn from treatment. Do not re-challenge with study treatment.
- Completed the “Safety Follow-up Procedures” listed below.
- Upon completion of the safety follow-up, the subject must be withdrawn from the study unless further follow-up is required.

Subjects with ALT > 3x ULN and bilirubin > 2x ULN (> 35% direct); or ALT > 3x ULN and INR > 1.5:

- **This event is an SAE** and should be reported using the SAE Reporting Form (reference [Section 11.2](#)). Serum bilirubin fractionation should be performed, if testing is available. If fractionation is unavailable, urinary bilirubin is to be measured via dipstick (a measurement of direct bilirubin, which would suggest liver injury).

Note: INR testing is not required per protocol and the threshold value does not apply to subjects receiving anticoagulants.

- Make every reasonable attempt to have the subject return to the clinic within 24 hours for repeat liver chemistries, additional testing and close monitoring (with specialist or hepatology consultation recommended).
- Monitor the subject twice weekly until liver chemistries (ALT, AST, alkaline phosphatase, bilirubin) resolve, stabilize or return to within baseline values.

Subjects with ALT > 5x ULN or ALT > 3x ULN who have hepatitis symptoms or rash, cannot be monitored for 4 weeks or have elevations that persist ≥ 4 weeks:

- Make every reasonable attempt to have the subject return to the clinic within 24-72 hours for repeat liver chemistries and additional testing.
- Monitor subject weekly until liver chemistries (ALT, AST, alkaline phosphatase, bilirubin) resolve, stabilize or return to within baseline values.

Subjects with ALT > 3x ULN and < 5x ULN and bilirubin < 2x ULN, who do not exhibit hepatitis symptoms or rash:

- Subject may continue study treatment, if liver chemistries (ALT, AST, alkaline phosphatase, bilirubin) can be monitored weekly for up to 4 weeks.

- If the subject later meets the liver chemistry stopping criteria (outlined in Section 6.4.5 of the protocol), immediately withdraw study treatment, perform additional testing and continue safety follow-up until liver chemistries resolve, stabilize or return to baseline values.

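### Exclusion 17 sets creatinine and INR limits that no protocol-required test measures before the first injection

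*Combined protocol and SAP*

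**What the plan says.** Section 5.3, exclusion 17, lists five laboratory limits. Three concern total bilirubin, ALT and AST. The other two read "serum creatinine $> 2xULN$, international normalized ratio (INR) $> 1.5xULN".

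Two places make the criteria a precondition. Appendix 1 footnote c: "Subjects will be included in the study only after it is determined that subject meets all inclusion criteria and none of the exclusion criteria". Section 9.3.1: "SUBLOCADE injection will be administered following confirmation that the subject meets all eligibility and continuation criteria". Section 6.1 adds that ineligible subjects should not receive the study injection and are to be recorded as screen failures.

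For Visit 1, Appendix 1 schedules one safety blood test, the STAT liver function tests, taken before the sublingual test dose. Footnote d says: "Samples must be drawn prior to dosing and will include ALT, AST and bilirubin". The injection is given at the same visit, on Day 1 (footnote f).

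Creatinine appears in the serum chemistry list of Table 1 (Section 8.5), next to "Calculated creatinine clearance". In Appendix 2 the general laboratory tests row is marked once, at Visit 2.

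INR is not in Table 1 or in any row of Appendix 1 or 2. Appendix 3 states that "INR testing is not required per protocol", and stopping criterion 1 in Section 6.4.5 uses it conditionally: "international normalized ratio (INR) >1.5 , if INR measured".

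**The concern.** An exclusion criterion works only if the information it needs is in hand when the decision is made. Here the decision comes before a long-acting injection, within a single visit. A site that performed every scheduled test and nothing more would have no creatinine or INR value at that point, yet would have to record that no exclusion applied.

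The first consequence is for subject protection: two stated safety limits could go unchecked. A creatinine value over the limit would surface only after dosing, and an INR over the limit might never surface.

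The second is for trial conduct and reporting. Section 8.11 treats any noncompliance with the protocol as a deviation, so a site following the schedule may accumulate eligibility deviations that it could not have avoided. A subject later found ineligible stays in the analysis: the Treatment Population (Section 14.4.1) is everyone who received at least one dose, and Section 6.4.1 does not replace subjects withdrawn after treatment.

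**Working it through.** This is a consistency check, and the plan gives no figure to reproduce. Each analyte in exclusion 17 was traced through Table 1 and the two schedules.

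| Analyte | Limit in exclusion 17 | In Table 1 | Named in the pre-dose panel (Appendix 1, footnote d) | First scheduled |
|---|---|---|---|---|
| Total bilirubin | ≥1.5 × ULN | yes | yes | Visit 1, before dosing |
| ALT | ≥3 × ULN | yes | yes | Visit 1, before dosing |
| AST | ≥3 × ULN | yes | yes | Visit 1, before dosing |
| Serum creatinine | >2 × ULN | yes | no | Visit 2 |
| INR | >1.5 × ULN | no | no | never |

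Scheduled before dosing: 3. First scheduled after dosing: 1. Never scheduled: 1. Total 3 + 1 + 1 = 5, so 2 of 5 limits have no protocol-required pre-dose result.

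**Timing of creatinine.** Visit 2 is Day 2 with a window of -0/+3 days, that is Day 2 to Day 2 + 3 = Day 5. The first injection is on Day 1. The first scheduled creatinine therefore falls 1 to 4 days after it.

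**Could routine results fill the gap?** Section 8 says an assessment already done as standard of care within the screening window need not be repeated. That allows an existing value to be used but does not require one to exist. The fallback in footnote d, for when research blood cannot be obtained, covers only liver function tests taken for clinical reasons. The third entry route in the synopsis (Study Design) admits people treated by EMS who refused transport and then present at the clinic. They have no ED or inpatient visit for that overdose and are the least likely to have either value on file.

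**A related difference in wording.** Footnote b requires the pregnancy result to be available and reviewed before the test dose. Footnote d requires the liver samples only to be drawn before dosing. Section 9.3.1 implies that the result must be known, but the schedule does not say so.

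**The case against.** A reader might infer that exclusion 17 cannot be applied at all, that no subject's eligibility can be confirmed, or that an irreversible product is given to all of the approximately 100 subjects unchecked. The documents do not support any of these.

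- Bilirubin, ALT and AST are drawn STAT before dosing, so three of the five limits can be checked.
- Footnote d says what the samples will include, which is not exhaustive wording.
- Many subjects enter after ED or inpatient care for the overdose, and Section 8 allows their routine results to count. Some may well have creatinine or INR on file.
- Section 6.4.5.1 allows surgical removal of the depot within 14 days of injection, and the first scheduled creatinine falls inside that period. The product is long-acting, not irreversible.
- The INR statements in Appendix 3 and Section 6.4.5 concern liver abnormalities during treatment, not screening.

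These points limit the claim but do not remove it. The row in question is for liver function tests, and open wording there does not make creatinine a required result. Permission to use routine values does not ensure that they exist. Surgical removal is a remedy after the event, reportable as an adverse event of special interest (Section 11.2.4), and not a form of screening. For INR, the finding rests mainly on its absence from Table 1 and from both schedules; the Appendix 3 note only confirms that absence.

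**Conclusion.** The contradiction stands. The protocol requires all eligibility criteria to be settled before inclusion and injection, but two of the five limits in exclusion 17, creatinine and INR, have no protocol-required pre-dose measurement. Creatinine first appears in the schedule after the first injection, and INR never appears.

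The supportable statement is that these two checks are not assured for any subject. It is not that they fail for every subject. The number affected depends on what routine care happened to measure, and the documents give no figure for that. They also give no rate of raised creatinine or INR in this population, so the number of ineligible subjects dosed cannot be estimated.

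The conclusion assumes that a site does the tests the schedule requires and no others, and that the laboratory manual, which is not among these documents, adds no pre-dose test. The point does not touch the primary endpoint, the propensity-weighted Cox analysis or the sample size in Section 14.2.

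**What to change.** Reconcile exclusion 17 (Section 5.3), Table 1 (Section 8.5), Appendix 1 footnote d, the laboratory rows of Appendix 2 and the INR note in Appendix 3, so that every analyte named in exclusion 17 has a required result available before the first injection. Whether the panel or the criterion changes is for the sponsor and the investigator to decide.

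The same edit can state in footnote d that results must be available and reviewed, as footnote b already does for the pregnancy test. If routine-care values are meant to satisfy the criterion, the text should say so and say what happens when there are none.

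The cost is amendment wording. If the panel changes, it is also up to two added analytes. These may need a separate sample in the cases footnote d foresees, where no research blood can be drawn.

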Appendix 2 - Treatment Clinic Schedule of Events – (Week 1 Day 2 – Week 25 Day 169)

Procedure / Assessment	Treatment Period									30-Day Safety Follow-up Telephone Call ^d
	Visit 12	Visit 13	Visit 14	Visit 15	Visit 16	Visit 17	Visit 18	Visit 19	End of Treatment / Early Term	
	Wk 11 D 71 (±4) D	Wk 12 D 78 (±4) D	Wk 13 D 85 (±4) D	Wk 14 D92 (-2/+4) D	Wk 16 D106 (±4) D	Wk 18 D120 (-2/+4 D	Wk 20 D134 (±4) D	Wk 22 D148 (-2/+4) D	Wk 25 D 169 (±4) D	Wk 29 Day 199 (±4) D
Counselling	X	X	X	X	X	X	X	X	X	
Urine Drug Screen	X	X	X	X	X	X	X	X	X	
Delay Discounting Task		X							X	
Opioid Demand Task		X							X	
OC-VAS ^a	X	X	X	X	X	X	X	X	X	
COWS	X	X	X	X	X	X	X	X	X	
TEA	X					X			X	
HCRUQ	X			X		X		X	X	
MSQ	X					X			X	
Employment Question	X					X			X	X footnote
AE Assessment	X	X	X	X	X	X	X	X	X	X
Concomitant Medications Assessment	X	X	X	X	X	X	X	X	X	
Vital Signs	X	X	X	X	X	X	X	X	X	
Urine Pregnancy Test ^b	X	X	X	X	X	X	X	X	X	X
SUBLOCADE Injection				X		X		X		
Liver function laboratory testing			X				X		X	

- OC-VAS will be assessed prior to SUBLOCADE injection
- Urine pregnancy test, only for females of child-bearing potential. Results will be obtained prior to SUBLOCADE injection.
- All subjects will receive a safety follow-up telephone call 30 days after their EOT/ET visit to assess AEs, SAEs, pregnancy status (if applicable) and concomitant medications. Subjects who decline to continue in MAT will receive monthly safety follow-up phone calls for an additional 5 months (6 months total) to assess SAEs, pregnancy status (if applicable) and concomitant medications.

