8.9 Health Economics and Outcomes Assessments

Health economics and outcomes assessments will be collected at the time points listed in [Appendix 1](#) and [Appendix 2](#).

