8.9.3 Medication Satisfaction Questionnaire

The MSQ is a single-item questionnaire that evaluates satisfaction with medication (Vernon 2010). It is a subject-completed instrument with the following response levels. Responses are ordinal but can also be categorized into satisfied (5-7), neutral (4), or dissatisfied (1-3). The MSQ has shown an acceptable reliability (ICC>0.80) and validity (known groups, convergent and divergent validity) based on a randomized controlled trial with 191 schizophrenia patients (Vernon 2010).

8.9.4 Work Productivity and Activity Impairment Questionnaire: Specific Health Problem (WPAI: SHP)

The impact of the disease and its treatment on work productivity and regular daily activities will be assessed by the WPAI Questionnaire (Reilly 1993). The WPAI questionnaire has 2 versions: WPAI-general health (WPAI-GH) and WPAI-Specific Health Problem (WPAI- SHP). In this study, WPAI-SHP will be used to target the measure to OUD. The WPAI-SHP has 6 items designed to measure employment, number of hours missed from work, and activity impairment during the past seven days due to the health problem. WPAI: SHP has been used among patients with OUD (Hoffman 2017).

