14.7.2.1 Health Economics & Outcomes Analyses

Treatment Effectiveness Assessment (TEA)

HEOR endpoints relating to the TEA will be described as change from baseline score to each follow-up assessment and end of treatment (EOT). Absolute scores by study visit will also be reported and compared between treatment groups. The absolute score and/or change from baseline score at EOT will be considered the primary variable of interest in these analyses.

Baseline will be defined as the last assessment on or before Week 3 Day 15±4 (Visit 4). (See Appendix 2- Treatment Clinic Schedule of Events)

MEDICATION SATISFACTION QUESTIONNAIRE (MSQ)

The percentage of subjects reporting each response on the MSQ will be reported by study visit and EOT. The percentage of subjects reporting that they are satisfied (score 5-7) at the EOT will be considered the primary variable of interest in these analyses.

WORK PRODUCTIVITY ASSESSMENT INSTRUMENT: SPECIFIC HEALTH PROBLEM (WPAI:SHP)

For the WPAI:SHP, the percentage of patients employed, percentage absenteeism, percentage work impairment, and percentage activity impairment will be reported at baseline, each follow-up assessment and EOT by treatment arm. The change in percent employed from baseline to each follow-up assessment will be assessed. Among those employed at baseline and the respective follow-up assessments, the changes from baseline in percentage absenteeism, percentage work impairment and percentage activity impairment at each follow-up assessment will be assessed. The change in percent employed from baseline to EOT; and among those employed at baseline and EOT, the changes in percentage absenteeism, percentage work impairment and percentage activity impairment from baseline to EOT will be considered as primary variables of interest in these analyses.

Baseline will be defined as the last assessment on or before Week 3 Day 15±4 (Visit 4). (See Appendix 2- Treatment Clinic Schedule of Events)

HEALTHCARE RESOURCE UTILIZATION QUESTIONNAIRE(HCRUQ)

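### WPAI:SHP is scheduled only at Visit 2, so the planned changes to end of treatment in absenteeism, work impairment and activity impairment cannot be computed

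*Combined protocol and SAP*

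**What the plan says.** Employment, presenteeism and absenteeism measured by WPAI:SHP are an exploratory objective (synopsis and section 2.3) and an exploratory endpoint (synopsis and section 3.3). Section 8.9.4 describes the instrument: "The WPAI-SHP has 6 items designed to measure employment, number of hours missed from work, and activity impairment during the past seven days".

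Section 14.7.2.1 sets the analysis. Besides percent employed, "percentage absenteeism, percentage work impairment, and percentage activity impairment will be reported at baseline, each follow-up assessment and EOT by treatment arm". It then names its main variables: change in percent employed and, among subjects employed at both times, the corresponding changes for the other three measures: "percentage absenteeism, percentage work impairment and percentage activity impairment from baseline to EOT will be considered as primary variables of interest in these analyses". The baseline value is the last assessment up to and including Visit 4 (Day 15 ± 4).

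Section 8.9 says where the timing is fixed: "Health economics and outcomes assessments will be collected at the time points listed in" Appendices 1 and 2. In those tables WPAI:SHP appears in one row, in the first half of Appendix 2, with one mark, at Visit 2. The second half of Appendix 2 (Visit 12 to the 30-day call) has no WPAI:SHP row. It has a row labelled "Employment Question".

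**The concern.** The analysis section needs repeated measurement of the full questionnaire, and the schedule provides it once, within the baseline window. A change score needs two values per subject. If nothing is collected after baseline, three of the four variables named for this instrument do not exist, and the part of the exploratory objective on presenteeism and absenteeism goes unanswered.

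The analysis cannot repair this. Section 14.8 does not impute missing data in general. The mixed model for repeated measures that section 14.7.2.1 uses by default for continuous outcomes would have no post-baseline observations to fit. Because the questionnaire has a seven-day recall, values not collected at the visit cannot be reconstructed later.

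**Working it through.** The plan states no figure to reproduce here. The check is a count of scheduled assessments against the assessments that the analysis needs.

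**Step 1. Read the schedule by column.** Each outcomes row in the two halves of Appendix 2 splits into ten cells under ten visit headings (Visits 2–11; then Visits 12–19, EOT/ET and the 30-day call). The marked visits are:

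| Row | First half of Appendix 2 | Second half of Appendix 2 |
|---|---|---|
| TEA | Visits 2, 4 | Visits 12, 17, EOT/ET |
| MSQ | Visits 2, 4 | Visits 12, 17, EOT/ET |
| HCRUQ | Visits 2, 4, 8 | Visits 12, 15, 17, 19, EOT/ET |
| WPAI:SHP | Visit 2 | no row |
| Employment question | no row | Visits 12, 17, EOT/ET, 30-day call |

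Appendix 1 (Visit 1) has no row for WPAI:SHP.

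**Step 2. Rule out a reading fault.** The cells line up with the headings, and the neighbouring TEA and MSQ rows show their follow-up marks. A lost mark would not explain why the later row carries a different name.

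**Step 3. Count what the analysis needs.**

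- Scheduled WPAI:SHP assessments in total: 1 (Visit 2, Day 2).
- In the baseline window (up to Visit 4): 1.
- After baseline: 1 − 1 = 0.
- At EOT: 0.

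**Step 4. Match this to the four planned changes from baseline to EOT.**

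| Variable | Baseline source | EOT source | Pairs available as scheduled |
|---|---|---|---|
| Percent employed | WPAI:SHP, Visit 2 | Employment question | obtainable, if the two questions match |
| Absenteeism | WPAI:SHP, Visit 2 | none | 0 |
| Work impairment | WPAI:SHP, Visit 2 | none | 0 |
| Activity impairment | WPAI:SHP, Visit 2 | none | 0 |

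Three of four variables have no pairs, whatever share of the planned 100 or so subjects is retained or employed.

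**The case against.** The strongest reply is that the employment question may be WPAI:SHP under a loose label. It sits directly below MSQ, where WPAI:SHP sits in the first half of the table. It falls on the same follow-up visits as TEA and MSQ. Its cell at the 30-day call points to a footnote that is not among those listed, so some explanation may be missing.

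This is possible, but nothing in the documents supports it. No section defines the question. Its label is singular and names only employment, while section 8.9.4 describes six items that also cover hours missed and activity impairment. If the full instrument was meant, the schedule still has to say so, because it governs what sites collect.

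Three points on the other side do stand:

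- The outcomes are exploratory. They do not appear in Table 2, and no power was claimed for them. Calling them primary has force only within the analysis of this instrument.
- Change in percent employed remains obtainable, so the work objective is only partly lost.
- A repair confined to section 14.7.2.1 would be incomplete, because the objectives, endpoints and section 8.9.4 also refer to the full instrument. The 30-day call needs attention as well.

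**Conclusion.** The concern holds. As written, the schedule and section 14.7.2.1 contradict each other. No post-baseline WPAI:SHP is scheduled, so the data for three of the four planned changes to EOT would be entirely absent. This rests on reading the employment question as not being the six-item instrument, which is the only reading that the text supports. The consequence is limited to this exploratory outcome; the primary, key secondary and safety analyses are untouched.

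**What to change.** **Preferred.** In Appendix 2, replace the employment question at Visit 12, Visit 17 and EOT/ET with the full six-item WPAI:SHP. At the 30-day call, either define the employment question and supply its footnote, or remove it. If the present question is a single item, the cost is 6 − 1 = 5 extra items at each of three visits, or 15 per subject who attends all three. TEA and MSQ are already collected at those visits. Subjects who have already passed a visit cannot be recovered for that time point, so the report should state how many had the instrument scheduled.

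**Fallback, if the instrument cannot be added.** Delete the absenteeism, work impairment and activity impairment analyses from section 14.7.2.1 and keep percent employed. Make the matching cuts in the synopsis and sections 2.3 and 3.3, and bring section 8.9.4 into line. Give the wording of the employment question and confirm that it matches the employment item asked at Visit 2; otherwise the change in percent employed compares two different questions. The cost is editorial, plus the loss of the presenteeism and absenteeism part of the objective.
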